6.1.1.6. Tapering of Itacitinib or Placebo and Treatment Duration

Systemic therapy for patients with moderate-to-severe chronic GVHD is generally recommended for at least 1 year (Flowers and Martin 2015). Participants enrolled in this study may continue on study treatment for a maximum total treatment duration of 36 months or until criteria for treatment discontinuation are met (see Section 7.1.1).

For participants who achieved CR or PR, the investigators may initiate a taper of itacitinib/placebo on or after Day 365 provided that therapeutic doses of systemic corticosteroids (ie, > 10 mg/day prednisone or prednisone equivalent) and other systemic immunosuppressive therapies have been discontinued for at least 3 months. For investigators wishing to initiate a taper of itacitinib/placebo at an earlier timepoint for participants achieving sustained CR, they may start taper between D180 and D365 provided that the participant is still in CR after at least 3 months off systemic immunosuppressive therapies including corticosteroids.

Investigators may begin to taper the dose of itacitinib/placebo by 1 dose level (eg, from 400 mg QD to 300 mg QD, 300 mg BID to 200 mg BID). Discontinuation or subsequent tapering (eg, from 200 mg QD to 100 mg QD, from 200 mg BID to 100 mg BID) may occur within 28 to 56 days after the initial taper, as appropriate.

Participants who complete itacitinib/placebo taper after an initial response (CR or PR) or discontinue early for reasons other than GVHD progression and with no requirement for new GVHD therapy will enter the safety and post-treatment GVHD follow-up (see Table 4 and Section 8.8.2).

A physiological dose of 6 to 8 mg/day of methylprednisolone (ie, 7.5-10 mg/day of prednisone) during itacitinib taper is allowed and will not be considered treatment failure. Hydrocortisone hemisuccinate may be used as physiological maintenance dosing.

If GVHD signs/symptoms worsen during the taper of itacitinib/placebo (ie, first flare), the dose may be escalated by 1 dose level. If the participant requires addition or initiation of a new systemic therapy or experiences subsequent flare, then the participant would be considered as having progression of disease and would be withdrawn from study treatment. A short pulse of corticosteroids may be used once, without being considered progression, as long as the dose does not exceed the corticosteroid dose on Day 1 and can be tapered to physiological doses of 6 to 8 mg/day of methylprednisolone (or 7.5-10 mg/day of prednisone) within 6 weeks from starting.

After completion of an itacitinib/placebo taper, if reappearance or worsening of cGVHD occurs, the participant may be treated per institutional practice.

Participants who do not achieve or maintain a CR or PR at Day 180 who are still receiving benefit from itacitinib/placebo per investigator clinical judgment may continue on study treatment for a maximum total treatment duration of 36 months.

If the participant is not receiving benefit from itacitinib/placebo per investigator judgment, the participant must discontinue study treatment and be treated per institutional practice. However, if mixed response or stable/unchanged disease is assessed, it is recommended that a new systemic therapy be initiated after confirmation at the next scheduled visit, at least 4 weeks later. These participants will be followed for survival.

6.1.2. Corticosteroids

Systemic corticosteroids (methylprednisolone or prednisone) should be administered as background reference therapy at a dose level that is commensurate with institutional guidelines based on organ involvement and severity of disease. Doses are expected to range from 0.5 mg/kg per day to 1.0 mg/kg per day prednisone (or methylprednisolone equivalent to prednisone dose) for moderate to severe disease; questions regarding doses outside this range may be discussed with the sponsor medical monitor. Doses of prednisone will be converted to methylprednisolone equivalents by multiplying the prednisone dose by 0.80. Prednisolone may also be used (at the same dose as prednisone).

Details regarding the corticosteroids that will be used in Parts 1/1 expansion and Part 2 of this study are provided in Table 16.

Table 16: Corticosteroid Treatment Details, Parts 1/1 Expansion and 2

	Study Treatment	
Study treatment name:	Corticosteroids (methylprednisolone, prednisone)	
Dosage formulation:	Varies based on form and country-specific requirements	
Unit dose strength(s)/dosage level(s):	Starting dose 0.5-1.0 mg/kg per day prednisone (or methylprednisolone equivalent to prednisone dose); may vary based on institutional practice	
Route of administration:	PO/IV	
Administration instructions:	Per prescribing information	
Packaging and labeling:	Varies based on form and country-specific requirements	
Storage:	Per prescribing information	

6.1.2.1. Methylprednisolone

6.1.2.1.1. Description

Methylprednisolone sterile powder is an anti-inflammatory glucocorticoid, which contains methylprednisolone sodium succinate as the active ingredient. Methylprednisolone sodium succinate, USP, is the sodium succinate ester of methylprednisolone, and it occurs as a white, or nearly white, odorless hygroscopic, amorphous solid. It is very soluble in water and in alcohol; it is insoluble in chloroform and is very slightly soluble in acetone.

6.1.2.1.2. Supply, Packaging, and Labeling

Investigators are responsible for ensuring that participants receive commercially available supplies of methylprednisolone for the duration of the study treatment period. Incyte may provide methylprednisolone where required by applicable law or regulation.

6.1.2.1.3. Storage

Methylprednisolone (unreconstituted product or solution) should be stored in accordance with local prescribing information.

6.1.2.2. Prednisone

6.1.2.2.1. Description

Prednisone is a white to off-white, odorless, crystalline powder. Tablets are typically white in color and contain lactose monohydrate, magnesium stearate, microcrystalline cellulose, pregelatinized starch, and sodium starch glycolate. Commonly available dose strengths include 1 mg, 2.5 mg, 5 mg, 10 mg, 20 mg, and 50 mg tablets.

6.1.2.2.2. Supply, Packaging, and Labeling

Investigators are responsible for ensuring that participants receive commercially available supplies of prednisone for the duration of the study treatment period. Incyte may provide prednisone where required by applicable law or regulation.

6.1.2.2.3. Storage

Prednisone tablets should be stored in accordance with local prescribing information requirements.

6.1.2.3. Corticosteroid Tapering

Tapering of corticosteroids should be initiated on Day 14 or attempted earlier during the second week of starting treatment per the following published recommendations (Flowers and Martin 2015). This guidance applies to all randomized participants (Table 17).

Table 17:	Corticosteroid Taperi	ng Guidelines
------------------	-----------------------	---------------

Study Day	Dose, mg/kg Body Weight	
1	Current QD dose of corticosteroid (eg, 1 mg/kg per day)	
7-14	Current dose of corticosteroid (eg, 1 mg/kg per day); Decrease alternate day dose by 50% (0.5 mg/kg per day)	
28	Current dose of corticosteroid (1 mg/kg per day); Decrease alternate day dose by 50% (0.25 mg/kg per day)	
42	Current dose of corticosteroid (1 mg/kg), QOD	
56	Decrease current dose of corticosteroid by 10% every week until off	

Although commercial supplies of corticosteroids will be used, dose changes and interruptions will also be documented in the medical record and monitored by the sponsor or its designee. As corticosteroid dose strengths and administration types will vary, compliance with corticosteroids will not be calculated.

6.1.2.4. Management of Corticosteroids During cGVHD Flare

If cGVHD flares during a corticosteroid taper, the dose of corticosteroids may be re-escalated at the investigator's discretion and will not be considered treatment failure. If the flare requires addition or initiation of new systemic therapy or re-escalation of prednisone or methylprednisolone at a dose exceeding the dose on Day 1, the participant will be considered to have experienced treatment failure and must be withdrawn from study treatment. The use of

systemic corticosteroids other than prednisone or methylprednisolone will not be considered initiation of new systemic therapy as long as the dose does is not higher than the equivalent prednisone dose on Day 1. This guidance applies to all randomized participants.

6.1.3. Prophylactic and Supportive Care Medications

Standard cGVHD prophylaxis and treatment medications initiated before randomization including CNIs (cyclosporine or tacrolimus), and topical/inhaled corticosteroid therapy may be continued per institutional guidelines. CNIs may be continued at the same dose or may be reduced per institutional practice or at a 25% dose reduction per month.

Patients who undergo allo-HCT are at risk for a variety of infections based on the degree of immunosuppression induced by the conditioning regimen before transplant. As such, it is considered routine practice to use antibiotics and anti-infectives as prophylactic therapies (Tomblyn et al 2009). In cases where post-transplant anti-infective prophylaxis measures are necessary, ongoing therapy may continue at the investigator's discretion per institutional guidelines.

6.2. Measures to Minimize Bias: Randomization and Blinding

All participants will be centrally assigned to study treatment using an IVRS. Before the study is initiated, the telephone number and call-in directions for the IVRS and/or the login information and directions for the IVRS will be provided to each site. Full details will be provided in the IVRS section of the Study Manual.

Study treatment will be dispensed at the study visits summarized in the schedule of activities (Table 4).

Returned study treatment should not be redispensed to the participants.

Centralized randomization numbers within each stratum will be created for treatment assignment. Participants will be assigned to study drug cohorts in accordance with the randomization schedule. In Part 1, the participant, the investigator, and the sponsor will be aware of each treatment assignment; in Part 2, they will remain blinded to treatment assignment.

6.3. Concomitant Medications and Procedures

All concomitant medications and treatments (including over-the-counter or prescription medicines, vitamins, vaccines, and/or herbal supplements) must be recorded in the eCRF. Any prior medication received up to 28 days before the first dose of study treatment and 30 days after the last dose of study treatment, or until the participant begins a new cGVHD therapy, whichever occurs first, will be recorded in the eCRF. Any addition, deletion, or change in the dose of these medications will also be recorded.

Concomitant treatments/procedures that are required to manage a participant's medical condition during the study will also be recorded in the eCRF. The medical monitor should be contacted if there are any questions regarding concomitant or prior therapy.

6.3.1. Permitted Medications and Procedures

As described in Section 6.1.3, continued use of agents administered as cGVHD prophylaxis, including agents used to prevent or treat infections, is permitted.

Additional supportive care measures (eg, transfusions, use of antiemetics and antimotility agents for diarrhea management) are permitted at the investigator's discretion.

6.3.2. Restricted Medications and Procedures

The following medications have restrictions on use during the treatment period of the study:

- Coadministration with potent CYP3A4 inhibitors, as follows:
 - Coadministration with posaconazole, itraconazole, voriconazole, ketoconazole, mibefradil, and clarithromycin. If the participant's medical condition requires treatment with any of these drugs, a dose reduction of itacitinib by 1 dose level as displayed in Table 13 and Table 14 should be performed.
 - The sponsor medical monitor may be consulted for advice when CYP3A inhibitors are considered.
- If concomitant administration of an anticoagulant/antiplatelet medication is indicated, then caution and enhanced monitoring is required. The presence and severity of thrombocytopenia should be a factor in the choice of anticoagulant and dose. Use of aspirin at doses > 81 mg per day should be avoided. Use of low-molecular-weight heparin is allowed.

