2.3.2.2. Rationale for Part 1 Expansion

Additional dosing regimens of itacitinib were selected for evaluation in combination with corticosteroids in an expansion to Part 1 of the study based on the following rationale:

- Study INCB39110-301 was a randomized, double-blind, placebo-controlled Phase 3 study evaluating itacitinib or placebo, in combination with corticosteroids, as a first-line treatment for participants with aGVHD. A total of 439 participants were randomized 1:1 to receive either itacitinib or placebo. The primary endpoint was ORR at Day 28, and the key secondary endpoint was nonrelapse mortality at Month 6. Although there was a higher ORR for itacitinib versus placebo (74.0% vs 66.4%, respectively), the result was not statistically significant (p = 0.08), and there was no difference in nonrelapse mortality (approximately 18% in both arms). There was a trend favoring itacitinib with regards to the rate of complete response (53% vs 41%, respectively); however, this was an unplanned, exploratory sensitivity analysis. The safety profile observed in GRAVITAS-301 was consistent with that observed in previously reported studies of itacitinib in combination with corticosteroids, and no new safety signals were identified. A preliminary exposure/response analysis demonstrated a statistically significant relationship between steady-state exposure and Day 28 ORR with response rates in participants in the upper tertile of exposure (ie, AUC $> \sim 6500$ nM·h) predicted to be > 90%.
- Preliminary exposure data from 21 participants enrolled in Part 1 of the current study showed that the majority (14/21) of participants had AUC ≤ 10,000 nM·h. Participants with relatively high exposures (AUC_τ > 20,000 nM·h) experienced Grade 3/4 AEs, mainly thrombocytopenia, that were manageable with dose reductions and/or discontinuations.
- At a dose of itacitinib of 400 mg QD, the predicted AUC in participants with chronic GVHD is approximately 20,000 nM·h. At a dosing/schedule of itacitinib of 300 mg BID, the C_{max} is predicted to be comparable with the observed value of 300 mg QD, with a higher daily AUC and trough approximately 3 times higher with BID dosing compared with QD; supporting more sustained inhibition of the target throughout the dosing interval.

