- Itacitinib doses as high as 400 mg BID and 600 mg QD have been studied in other patient populations, for example, rheumatoid arthritis, plaque psoriasis, and myelofibrosis and were well-tolerated with manageable AEs (additional information can be found in the IB).

Considering the dose range and the corresponding safety profile across patients with acute and chronic GVHD and other autoimmune and oncology populations, doses of 400 mg QD and 300 mg BID were selected for further evaluation in an expansion to Part 1 of the

study (additional dose cohorts of 35 participants each). The original cohort of 300 mg QD will also be expanded to provide a more robust safety and efficacy assessment of this dose level; Part 1 expansion will also include 1 cohort of corticosteroids as single-agent for a contemporary comparison of the safety and efficacy of each combination cohort. Data from Part 1 expansion will guide dose selection for Part 2 of the study.

Itacitinib doses should be adjusted to maintain a consistent exposure with concomitant use of a strong CYP3A inhibitor; see Section 6.1.1.5 for more information.

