2.3.2.4. Dose Modifications for Concomitant Medications

Observed data from Study INCB 39110-108 suggest that there is an approximate 2-fold increase in exposure when itacitinib is coadministered with a potent CYP3A4 inhibitor (posaconazole in the majority of cases; DMB-18.60.1). This was further supported by preliminary data from Study INCB 39110-301, in which the magnitude of increase in itacitinib exposure with coadministration of strong CYP3A inhibitors (ie, posaconazole or voriconazole) was 1.65- to 2.55-fold (DMB-20.35.1). However, preliminary PK data from Part 1 and the Part 1 expansion in this current study in participants with cGVHD demonstrated a larger impact of the strong CYP3A inhibitors than observed in the aGVHD population. From Table 5, it can be seen that the current dose reductions did not normalize the exposure within a given treatment arm. For example, a dose reduction to 300 mg QD with concomitant administration of a strong CYP3A inhibitor resulted in a geometric mean AUC₀₋₂₄ that was still 2.4 to 2.9 times greater than that of the 400 mg QD dose administered without a strong CYP3A inhibitor. Similarly, a dose reduction to 200 mg QD with a strong CYP3A inhibitor resulted in an exposure 2.3 to 2.4 times that of the 300 mg QD dose alone. From Table 5, however, a dose of 200 mg QD with a strong CYP3A inhibitor has an exposure that approximates that of 400 mg QD alone. In this patient population (ie, cGVHD), a greater dose reduction is recommended when coadministering itacitinib with a strong CYP3A inhibitor; 400 mg QD to 200 mg QD or 300 mg QD to 100 mg QD. More detailed dosing information is provided in Table 13 and Table 14.

Table 5: Preliminary PK Parameters From Part 1 and Part 1 Expansion by Dose, Strong CYP3A Inhibitor Coadministration Status, and Day

		200 m	ng QD	300 m	ng QD	400 m	ng QD	200 m	g BID	300 mg BID	
	Day	No	Yes	No	Yes	No	Yes	No	Yes	No	Yes
AUC ₀₋₂₄	7	4230 (2370), 3720 [6]	14,800 (10,800), 11,400 [16]	5850 (3980), 4680 [15]	29,500 (14,300), 25,500 [11]	10,200 (5250), 8800 [13]	23,700 (28,700), 13,600 [3]	_	38,200 (24,600), 32,600 [8]	14,880 (10,280), 12,120 [9]	_
	28	6300 (4230), 5220 [6]	15,100 (7630), 13,300 [15]	6670 (3730), 5690 [10]	29,900 (17,200), 21,200 [12]	10,300 (5690), 8880 [10]	_	_	40,800 (34,200), 32,000 [4]	19,020 (11,260), 16,740 [7]	_

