6.1.1.3. Dose-Limiting Toxicity Assessment

Dose-limiting toxicity will be defined as the occurrence of any of the toxicities in Table 12 with onset up to and including Day 28, except those with a clear alternative explanation. All DLTs will be assessed for severity by the investigator using CTCAE v4.03 criteria. Participants who receive at least 21 of 28 doses of study drug at the level assigned or have a DLT will be

considered evaluable for determining tolerability of the dose. Participants who do not achieve this duration of exposure and do not have a DLT will be replaced for purposes of toxicity identification. CYP3A inhibitors may be used during the DLT assessment window (ie, first 28 days of study treatment) with appropriate dose reductions for itacitinib, according to Table 13 and Table 14.

Individual dose reductions may be made based on events observed at any time during treatment with study drug.

Table 12: Definitions of Dose-Limiting Toxicity

Toxicity	Definition
Nonhematologic	• Any ≥ Grade 3 nonhematologic toxicity that can be reasonably attributed to study treatment. ≥ Grade 3 nonhematologic clinical findings that may be related to underlying GVHD (eg, nausea, vomiting, diarrhea, rash, dry eye) will not be considered as DLTs.
	 Any ≥ Grade 3 clinical chemistry laboratory abnormalities that are considered clinically significant and related to study treatment. Transient laboratory abnormalities not associated with clinically significant signs and symptoms, manageable with adequate medical care, and not leading to hospitalization will not be considered as DLTs.
Hematologic	• Grade 4 neutropenia lasting more than 7 days or a ≥ 90% decrease in ANC from baseline that can reasonably be attributed to study treatment.
	• Platelet count $< 10 \times 10^9$ /L related to study treatment that does not recover to at least 20×10^9 /L after 2 weeks with no requirement for platelet transfusion in the preceding 3 days.

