Treatment Group A	300 mg QD	100 mg QD	200 mg QD	Discontinue	100 mg QD	Discontinue
Treatment Group B	400 mg QD	200 mg QD	300 mg QD	100 mg QD	200 mg QD	Discontinue
Treatment Group C: Discontinued as of SEP 2021	300 mg BID	200 mg BID	200 mg BID	100 mg BID	100 mg BID	100 mg QD

sCYP3A4 = strong CYP3A4 (ie, posaconazole, itraconazole, voriconazole, ketoconazole, mibefradil, clarithromycin).

Table 15: Itacitinib/Placebo Dose Modification Guidelines

ADVERSE EVENT	ACTION TAKEN	
Chemistry		
AST and/or ALT > 3.0 × ULN that occurs in the presence of GVHD response and cannot be attributed to new liver GVHD or concomitant therapy.	 Interrupt for up to 21 days until the toxicity has resolved to ≤ Grade 1. Exceptions require sponsor approval. Monitor AST/ALT on a weekly basis. Restart at previous dose. If assessed as related to itacitinib/placebo, restart at next lower dose and monitor as clinically indicated. 	
AST and/or ALT > 3.0 × ULN that occurs in participants with liver GVHD and cannot be attributed to worsening of liver GVHD or concomitant therapy.	 Repeat assessment within 7 days. If elevation persists: Reduce dose by 1 dose level. For participants receiving 300 mg QD or higher, a second dose reduction may be considered. Resume previous dose if AST and/or ALT ≤ 3.0 × ULN. 	

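### Protocol Section 6.3.2 asks for a one-level dose cut with a strong CYP3A4 inhibitor, but the Table 14 it cites requires two levels for Treatment Groups A and B

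*Protocol*

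**What the plan says.** Section 6.3.2 of the protocol names six potent CYP3A4 inhibitors. If a participant needs one of them, "a dose reduction of itacitinib by 1 dose level as displayed in Table 13 and Table 14 should be performed". The footnote to Table 14 in Section 6.1.1.5 lists the same six drugs, so both places govern the same situation.

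Table 14 has a separate column for dosing with an inhibitor. Its starting doses there are 100 mg QD for Group A (300 mg QD without an inhibitor) and 200 mg QD for Group B (400 mg QD without).

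Section 2.3.2.4 gives the reason. From the PK data in Table 5, "it can be seen that the current dose reductions did not normalize the exposure within a given treatment arm". It therefore recommends a larger cut when "coadministering itacitinib with a strong CYP3A inhibitor; 400 mg QD to 200 mg QD or 300 mg QD to 100 mg QD".

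The stated aim is in Section 2.3.2.2: "Itacitinib doses should be adjusted to maintain a consistent exposure with concomitant use of a strong CYP3A inhibitor".

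**The concern.** The sentence in Section 6.3.2 is the operating instruction for starting an inhibitor during treatment. For the two itacitinib groups still being compared, it contradicts the table it cites. Its words describe the one-level reduction that Section 2.3.2.4 found insufficient.

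Following the words doubles the intended dose in Group A (200 against 100 mg QD) and gives 1.5 times the intended dose in Group B (300 against 200 mg QD). Section 2.3.2.2 reports Grade 3/4 events, mainly thrombocytopenia, in Part 1 participants with AUC above 20,000 nM·h. It adds that these were manageable with dose reductions or discontinuation.

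The phrase can also mislead the other way. A reader told to go down one level might use Table 14's first-reduction column with inhibitor, which gives 100 mg QD for Group B and discontinuation for Group A.

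Part 1 expansion is used to choose the Part 2 dose, so uneven dosing with inhibitors would also blur the exposure difference between the groups.

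**Working it through.** **1. Size of one level.** The taper example in Section 6.1.1.6 treats 400 to 300 mg QD as one level. The no-inhibitor steps in Tables 13 and 14 also fall by 100 mg.

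**2. Levels down to the with-inhibitor starting dose.**

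| Group | Steps without inhibitor | Start with inhibitor | Levels down |
|---|---|---|---|
| Part 1, 200 mg QD | 200, 100 | 100 mg QD | 1 |
| Part 1, 300 mg QD | 300, 200, 100 | 200 mg QD | 1 |
| A | 300, 200, 100 | 100 mg QD | 2 |
| B | 400, 300, 200 | 200 mg QD | 2 |
| C (discontinued) | 300, 200, 100 BID | 200 mg BID | 1 |

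The mismatch is confined to Groups A and B.

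**3. Reproducing the plan's exposure figures.** The inputs are the Table 5 geometric mean AUC0-24 values. Each ratio is the reduced dose with inhibitor divided by the full dose alone.

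- Group B, one level (300 mg with inhibitor against 400 mg alone): 25,500/8,800 = 2.90 on Day 7; 21,200/8,880 = 2.39 on Day 28. Section 2.3.2.4 states 2.4 to 2.9.
- Group A, one level (200 mg with inhibitor against 300 mg alone): 11,400/4,680 = 2.44 on Day 7; 13,300/5,690 = 2.34 on Day 28. Section 2.3.2.4 states 2.3 to 2.4.

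Both stated ranges are reproduced.

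**4. At the Table 14 dose.** Group B (200 mg with inhibitor against 400 mg alone): 11,400/8,800 = 1.30 and 13,300/8,880 = 1.50. Table 5 has no 100 mg QD cell with inhibitor, so no observed figure exists for Group A.

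**5. Words against table, Group B directly.** 25,500/11,400 = 2.24 on Day 7 and 21,200/13,300 = 1.59 on Day 28. Approximate 95% intervals are 1.36 to 3.69 and 0.90 to 2.83. They use a Welch t interval on the log scale, assume log-normal AUC, and take the log variance as 2 × ln(mean/geometric mean). The Day 28 cell for 300 mg with inhibitor fits a log-normal poorly, and the Day 28 interval includes 1.

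**6. How often the rule is needed.** On Day 7, 16 + 11 + 3 + 8 = 38 of 81 AUC profiles were taken with an inhibitor (47%; exact 95% interval 36% to 58%). This pools Part 1, every dose level and the BID group.

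**7. New starts remaining.** At the 09 JUL 2021 cutoff (Section 2.3.2.3), 32 participants were in Group A and 25 in Group B, against a limit of 35 each. That left at most 3 + 10 = 13 new starts. Participants already on treatment who later need an inhibitor come on top of these.

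**The case against.** The protocol already gives the right dose in several places. Section 6.3.2 itself points to the tables, and Table 14 prints the dose in mg in a dedicated column. Section 2.3.2.4 repeats it in words. Section 6.1.1.3 allows inhibitors "with appropriate dose reductions for itacitinib, according to Table 13 and Table 14" without counting levels, and the medical monitor may be consulted. A wrong dose requires a site to count levels and overlook the cited cell. Few new starts in A and B remained.

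The exposure data are also thin. They compare different participants, with 10 to 16 profiles in each cell used here. One cell does not fit the pattern: 400 mg QD with inhibitor on Day 7 has a geometric mean of 13,600, which is 13,600/8,800 = 1.55 times 400 mg alone and about half the value at 300 mg with inhibitor. It rests on three profiles with an SD of 28,700, so it settles little, but exposure does not rise steadily with dose in this table.

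Exposure at the one-level dose is also not far from what was planned for. Section 2.3.2.2 says "At a dose of itacitinib of 400 mg QD, the predicted AUC in participants with chronic GVHD is approximately 20,000" nM·h. If Table 5 uses the same unit, which it does not state, the 21,200 to 25,500 seen at 300 mg with inhibitor is close to that prediction, though well above the roughly 8,800 observed.

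These points limit how often and how seriously the sentence would mislead. They do not remove the contradiction. The words and the cited table still give different doses for A and B, and the monitor consultation is optional.

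**Conclusion.** Wrong as written, for Treatment Groups A and B. The number of levels in Section 6.3.2 disagrees with Table 14 and Section 2.3.2.4. Following it would give the reductions that the protocol says left exposure at 2.3 to 2.9 times that of the full dose alone. For Group B the tabulated dose brings this to about 1.3 to 1.5 times. The dose mismatch needs no assumption. The exposure sizes rest on the small between-participant comparisons in Table 5.

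The documents do not support several stronger readings that a reader might infer:

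- **Participants have been overdosed because of this sentence.** The documents hold no record of misapplication, and its rate is unknown. Section 2.3.2.4 presents the Table 5 exposures as the result of the reductions then in force.
- **About 47% are at risk of a wrong dose.** That figure shows how often an inhibitor was in use, not how often the rule is misread.
- **The wording bears on the relapse signal.** The relapse concern arose in the BID group, and nothing in the documents links relapse to inhibitor dosing.
- **Table 13 is also wrong.** Its 300 mg QD row keeps 200 mg QD with an inhibitor, whereas Section 2.3.2.4 says 100 mg QD. But that section refers onward ("More detailed dosing information is provided in Table 13 and Table 14"), and keeping the old dose for the small Part 1 cohort may be deliberate.
- **Part 2 lacks a rule.** Its dose is not yet chosen, so a missing Part 2 row is not an error now.

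**What to change.** In Section 6.3.2, delete the level count and write: *reduce itacitinib to the With-sCYP3A4 dose in Table 13 or Table 14 for the participant's treatment group, at the participant's current reduction step (starting dose, first or second reduction); former Group C participants now on 400 mg QD follow the Group B row.*

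The reduction step has to be named because Table 14 gives a with-inhibitor dose at each step. The Group C clause is needed because Table 10 moves those participants to the 400 mg QD instructions, while their own row in Table 14 would still give 200 mg BID.

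The cost is one sentence, in a clarification letter or the next amendment, with IRB/IEC approval under Section 11.1 if made by amendment. It needs no new procedures or data. It does not undo the mixed exposures among participants dosed under the earlier reductions.
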